Whether or not elective irradiation of pelvic nodes (ENI) provides any benefit over exclusive RT to prostate only, has been a longstanding therapeutic dilemma [7] being still now increasingly discussed in the modern radiotherapy scenario [8, 9]. Data obtained from international literature are still controversial and ENI is not clearly linked to relevant advantages in terms of overall survival (OS) according to the few randomized clinical trials available [10] and to recent reviews [7, 11, 12, 13, 14, 15], particularly if Whole Pelvic Radiation Therapy (WPRT) is associated with ADT.

In fact, in the radical setting, the addition of ADT to RT (but not to RP) is linked to a survival benefit in men with intermediate- or high risk disease according to Level I evidence; to date, however, it remains unclear whether this benefit is driven by an effect on micro metastatic disease in the pelvic lymph nodes and/or bones, by hormonal radio sensitization of the primary tumour, or by some combination thereof [16, 17, 18, 19]. Consequently, neoadjuvant (NHT), concomitant, or adjuvant

(AHT) androgen deprivation therapy (ADT) is recommended for selected men with unfavourable intermediate-risk or high risk disease. Long-term ADT is indicated in patients with a high/very high risk of disease recurrence and typically consists of NHT plus RT followed by AHT (for 2-3 years) [20, 21, 22, 23]. Conversely, the addition of RT to ADT is related to a significant reduction of cause-specific and all-cause mortality (OS) in comparison with exclusive systemic treatments [24, 25].

Elective nodal irradiation and evolving treatment techniques

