In the adjuvant setting, sterilizing microscopic disease potentially persistent after radical surgery, particularly in high-risk patients, represents the rationale of adding WPRT to prostatic bed radiotherapy in pN0 patients. Goldner et al. evaluated the clinical impact of prostate only adjuvant RT in pN0 patients showing a 5-year biochemical relapse free survival of 100% and 58% in patients with a risk of nodal involvement <15% and >15%, respectively. These findings may be explained by a microscopic involvement of pelvic structures (lymph nodes, bone) other than prostate bed. However, the role of adjuvant post-surgical WPRT need to be validated by large prospective studies, not actually ongoing to our knowledge. [37, 38, 39, 40]. Moreover, no clear-cut guidelines are available about the usefulness of adding ADT to adjuvant RT in the different subsets of pN0 patients.

On the other hand, nodal involvement (pN1) is a strong negative prognostic factor and adjuvant RT in these patients may be useful to optimize loco-regional control deferring first or second line systemic therapies [41]. Actually, the standard adjuvant treatment for pN1 PCa patients is represented by long term ADT, but the association with WPRT might significantly increase survival outcomes [42]. A recent analysis conducted by SEER on “pN1 M0” PCa patients treated with adjuvant WPRT seems to confirm the benefit obtained by the association of WPRT with ADT, demonstrating a survival advantage for intermediate risk patients [43].

Conclusions, rationale and summary of the study

In conclusion, open questions about ENI for prostate cancer still remain:

1. In the exclusive radiotherapy scenario, does ENI produce an overall or biochemical relapse free survival advantage over prostate only radiotherapy for intermediate/high/very high risk cases?
2. If ADT is added to prostate only radiotherapy, in intermediate/high/very high risk cases, ENI is any longer needed?

3. Is ENI, associated or not to ADT, linked with an OS or bRFS survival advantage in patients submitted to adjuvant postsurgical prostate radiotherapy?
4. Additional toxicity due to the larger volumes treated might be reduced by more sophisticated radiotherapy techniques when ENI is added to prostate?
5. How many Radiation Oncology centers use ENI to treat patients with intermediate/high/very high-risk prostate cancer, with or without ADT?

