Centers involved will identify all the eligible cases with biopsy proven prostate adenocarcinoma. Patients who are candidate to get involved in the study will be contacted by the physician in charge of the study for each Center. **Every** prostate cancer patient consecutively evaluated at the recruiting Centers and planned to receive radical exclusive or post-operative radiotherapy will be registered; this registration includes demographic and staging results data; only intermediate, high, very high patients will have, however, treatment and follow up CRF compiled (both treated with or without ENI; +/- ADT).

Eligible patients will then receive all the information necessary to formulate their adhesion to the study and finally the physician will fill in the “Pretreatment” Case Report Form (CRF) that will include:

- Demographic Information (date of birth, study title, civil state, working information);
- Another person (relatives, friends,...) as a contact to minimize follow up loss;
- Anamnestic data (height, weight, smoking habit, comorbidities, Cumulative Illness Rating Scale [44], Attachment 1);
- Initial diagnosis (date; PSA at diagnosis);
- Risk factors;
- Staging (clinical TNM, date of biopsy, Gleason score, total number of samples, number of positive samples);
- Quality of life and symptoms caused by prostate cancer (using Italian UCLA Prostate Cancer Index) [45, 46];
- General quality of life (SF-12 Standard V1) [47].

The choice of the treatment will be done based on commonly used international guidelines and on the specific internal protocol of each participating Center.

Since this study is observational, involved patients will be treated following *good clinical practice* and institutional policies procedures.

Clinical outcomes, (such as overall survival and biochemical relapse free survival) and variables, demographic features, dosimetric analysis and acute/late toxicities of both RT and ADT will be reported.

Phase 3: Follow-up (1, 3, 6, 12, 18, 24, 30, 36 months)

After the end of the radiotherapy treatment patients will be evaluated 1, 3, 6, 12, 18, 24, 30 and 36 months since the last session.

Every patient will be contacted by the physicians to fill a CRF that will include:

- Vital state (mortality, date and causes of death) or loss to follow up;
- Last PSA value;

- Other treatments (drugs);

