- Treatment : type of treatment, start date, PSA value before treatment; if surgery type of surgery and pathological TNM, margins, Gleason Score, number of positive lymph nodes; if external RT (intent, modality, technique, dose/fraction, volumes, concomitant hormonal therapies); if brachytherapy (type, intent, dose); if hormone therapy (type of drugs, start and end date, total duration);
- Acute and late toxicities;
- Biochemical Relapse with PSA value and date of last PSA;
- Quality of life and symptoms due to prostate cancer (Italian UCLA-PCI);
- General quality of life SF-12.

Toxicity and response evaluation

The enrolled patients will undergo the first follow up visit one month after the end of radiotherapy. On that occasion, clinical examination will be performed and previously prescribed blood tests, if required, will be evaluated. Genitourinary and gastrointestinal toxicity due to radiation therapy for prostate cancer will be reported according to the NCI Common Terminology Criteria for Adverse Events (CTCAE) version 4 for adverse event (AE) reporting. The CTCAE version 4 is identified and located on the CTEP web site at:

http://ctep.cancer.gov/protocolDevelopment/electronic_applications/ctc.htm [48]

In addition, a Case Report Form (CRF) will be completed (see Attachment 2), regarding:

- Technical characteristics of the radiation treatment (dose, volume, technique, association or not with hormonal therapy);
- Quality of life and complications due to prostate cancer (according to Italian UCLA-PCI) [45, 46];
- General quality of life (SF-12 Standard V1) [47].

Thereafter patients will be evaluated at 3-months, 6-months and 12-months after the end of radiotherapy, and then every 6 months for at least 24 months. During all those scheduled follow up visits, PSA level (jointly with testosterone, in case of association with hormonal therapy) and

previously prescribed blood texts if required, will be evaluated. Patients will undergo clinical examination, and genitourinary and gastrointestinal toxicity will be assessed according to the CTCAE v4.0 classification scale). In addition, a CRF (see Attachment 3) will be completed at each visit, regarding:

- Survival status (mortality, date and cause of death) or exit from the study;
- If macroscopical recurrence or disease progression occurred, the radiological exams (if performed);
- Further treatments received/planned after radiotherapy;
- The last available PSA;

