- Quality of life and complications due to prostate cancer (Italian UCLA-PCI) [45, 46];
- General quality of life (SF-12 Standard V1) [47].

The Italian UCLA-PCI and SF-12 Standard V1 questionnaires reported in Attachment 2 and Attachment 3 [45, 46, 47] will be given by the referring physician and self-compiled by patients in physician's absence, eventually with the help of a nurse if necessary; thereafter, the referring physician will insert the data to the database.

Data Collection, Confidentiality

Data will be collected through an *ad hoc* web based software, built to guarantee:

1. Respect of the Italian laws and of the international rules about GMP and privacy, according also to the general principles fixed by the Helsinki declaration and its subsequent updates;
2. The anonymization of the patient records;
3. The possibility for each participating Center to have unrestricted access to its own data;
4. The restriction of the access to the full dataset composed by the sum of the records provided by the single Centers; this will be allowed only after the authorization of the PI and the Study Coordinator. Once the study will be completed, access to the whole database will be possible only after having obtained the authorization of the AIRO President in charge and of the AIRO Board;
5. The safe storage of the data, along with that of the previous AIRO-PCSG studies, along with.

The use of the software will be elucidated to the single participating Centers in *ad hoc* start up

meetings, to guarantee an appropriate and homogeneous data collection; a tool bar will however be devised, to automatically verify inconsistencies in the data collected.

Statistical Considerations

Sample size

From previous experiences of the AIRO PCSG [49, 50], at least 15-20 Radiotherapy Centers from different regions of the country will be able to participate to the study. It is conceivable an accrual of at least 400-500 patients within 2 years and a further follow up of at least 3 years for each patient. For intermediate and high risk patients, an overall survival at 5 years of 0.8 has been previously reported (RTOG 94-13) [51]. According to the primary end-point of the study, a sample size of 400 patients will allow to estimate a 5-year survival of 0.8 with 95% confidence interval of 0.76-0.84 [52].

Statistical Analyses

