In order to describe the data, mean and standard deviation will be used for normally distributed continuous variables, median and ranges for non-normally distributed continuous variables, proportions and percentages for categorical variables. Associations between two categorical variables will be assessed through the Pearson's chi-squared test or Fisher test, when appropriate. Differences between two-sample central tendencies will be assessed with a two independent sample t-test or Mann-Whitney U test or Wilcoxon, depending on distribution of the continuous variable.

Analysis of variance and covariance and regression models will be used for evaluating the associations of some variables with survival taking account of possible confounders.

In order to compare groups in terms of survival end-points, Kaplan-Meier curves will be estimated and log-rank tests will be performed.

Periodical analyses are planned in order to check the quality of entered data.

The analyses will be performed by using STATA 13 (StataCorp. 2013. Stata Statistical Software: Release 13. College Station, TX: StataCorp LP) or SPSS Statistical Software.

Ethical committee

After the final approval by the AIRO-PCSG, the Protocol will be submitted to the Ethical Committee (EC) of the Study Coordinating Centre; when it will be approved, the single participating Centres will consequently apply for approval of their EC. According to the judgment of the PI and of the Study Coordinator, the first patient will be enrolled when a sufficient number of Centres will have obtained EC approval. This will be the starting date for the study.

The present study will be performed in accordance with the present protocol, with the principles of Good Clinical Practice in the respect of the ICH GCP guidelines and the ethical principles contained in the Helsinki declaration.

Publication rules

Interim and final results of the study will be published under the final responsibility of the PI and of the Study Coordinator.

The following publication rules will be enforced:

1. The participating Centers should approve the paper;
2. Only Centers contributing to more than 5% of the cases collected will have a person quoted as Author of the paper; however, every Center contributing to the common database, as well as the people working to realize the Study, will be publicly quoted and their contribution acknowledged in the paper;
3. Authorship is granted in proportion to:
 - a. the cases contributed to the database;

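### Biochemical relapse-free survival is compared over 36 months with no term for androgen deprivation, although long-term ADT can fill 24 to 36 of those months, so unequal ADT use can bias the ENI comparison

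*Combined protocol and SAP*

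**What the plan says.** - **Follow-up.** Phase 3: "After the end of the radiotherapy treatment patients will be evaluated 1, 3, 6, 12, 18, 24, 30 and 36 months since the last session". Two other sections give this as a minimum: Sample size has "a further follow up of at least 3 years for each patient", and Toxicity and response evaluation has, after month 12, "then every 6 months for at least 24 months". No visit after month 36 is scheduled. The Attachment 3 title lists month 9 and omits month 30, so it does not match Phase 3.
- **ADT.** The Background, on ENI and hormonal manipulation, states: "Long-term ADT is indicated in patients with a high/very high risk of disease recurrence". It adds that this "typically consists of NHT plus RT followed by AHT (for 2-3 years"). Treatment is not assigned by the study (Phase 2): "The choice of the treatment will be done based on commonly used international guidelines and on the specific internal protocol of each participating Center".
- **Questions.** bRFS is a secondary endpoint. Questions 1 and 3 of the rationale name it for ENI. Question 2 asks: "If ADT is added to prostate only radiotherapy, in intermediate/high/very high risk cases, ENI is any longer needed".
- **Analysis.** Statistical Analyses: "In order to compare groups in terms of survival end-points, Kaplan-Meier curves will be estimated and log-rank tests will be performed". Regression allowing for possible confounders is also planned. Neither sentence names ADT, and the text gives no PSA threshold, time origin or rule for PSA measured under ADT.
- **Data.** The forms collect ADT type relative to radiotherapy (Attachment 2, one month), its start date, whether it continues, and its end date (Attachment 3). Testosterone is to be evaluated with PSA in men on hormonal therapy. No analysis is said to use these items.

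**The concern.** If PSA is suppressed during ADT, a man still on ADT has little chance of being recorded as a biochemical relapse. Men on long-term ADT and men on radiotherapy alone would then share the same 36-month clock with very different chances of showing an event. If ENI and long-term ADT tend to be given to the same men, which nothing in the design prevents, an ENI versus no-ENI log-rank test partly measures who is still on ADT. The study is meant to inform a later randomised trial of ENI, so a false bRFS signal, or a real one obscured, would carry into that design.

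**Working it through.** **The plan's own figure.** The only sizing figure concerns overall survival: 0.8 ± 1.96 × √(0.8 × 0.2/400) = 0.8 ± 0.039, or 0.761 to 0.839. This reproduces the stated 0.76 to 0.84. There is no such figure for bRFS.

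**Off-ADT observation, from the documents.** Window = 36 − months of adjuvant ADT.

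| Adjuvant ADT | Off-ADT months | Phase 3 visits left | Attachment 3 visits left |
|---|---|---|---|
| none | 36 | all 8 | all 7, after the 1-month form |
| 24 months | 12 | 30, 36 | 36 |
| 30 months | 6 | 36 | 36 |
| 36 months | 0 | none | none |

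**Assumptions for size; none is in the documents.** No ENI effect; constant and equal relapse hazard; 36-month off-ADT bRFS 0.80; full PSA suppression on ADT; 200 men per group; long-term ADT in 70% of ENI and 30% of non-ENI men, or 60% and 40%. Two models bracket what happens when ADT stops:

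- *Delay*: relapse is postponed by the whole ADT time.
- *Hiding*: relapse occurs on time but is seen no earlier than 3 months after ADT stops.

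**Expected 36-month relapse.** The hazard is −ln(0.80)/3 = 0.0744 per year.

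- Without ADT: 20%.
- 24 months, delay: 1 − exp(−0.0744 × 1) = 7.2%. 30 months, delay: 1 − exp(−0.0744 × 0.5) = 3.7%.
- 24 or 30 months, hiding: 20%, because everything surfaces by month 27 or 33.
- 36 months, either model: 0%.

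**Spurious ENI difference at 70%/30%** = 0.40 × (20% − relapse in ADT men). This is 5.1 points (24 months, delay), 6.5 (30 months, delay), 0 (24 or 30 months, hiding) and 8.0 (36 months, either model). At 60%/40% the multiplier is 0.20, giving 4.0 points for 36 months.

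**Simulated log-rank rejection at nominal 5%.**

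| ADT duration | Model | 70%/30% | 60%/40% |
|---|---|---|---|
| 24 months | delay | about 33% | about 11% |
| 30 months | delay | about 55% | about 18% |
| 24 or 30 months | hiding | about 5-6% | about 5% |
| 36 months | either | about 77% | about 26% |

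With equal ADT shares rejection is about 5%, so imbalance is what creates the false signal.

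**Sensitivity to the relapse rate.** The assumed 0.80 at 36 months equals 0.80^(60/36) = 0.69 at five years. With five-year bRFS of 0.80 or 0.58 (the latter is the lower figure cited in the Background), 36-month ADT at 70%/30% gives rejection of about 55% or 90%.

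**Direction.** Suppose long-term ADT men have twice the hazard (an assumption), at 70%/30%.

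- *24 months, hiding.* Relapse in ADT men is 1 − 0.80² = 36%. ENI: 0.7 × 36 + 0.3 × 20 = 31.2%. Non-ENI: 0.3 × 36 + 0.7 × 20 = 24.8%. ENI looks worse by 6.4 points, which is ordinary confounding by risk.
- *24 months, delay.* Relapse in ADT men is 1 − exp(−0.1488) = 13.8%. ENI: 15.7%. Non-ENI: 18.1%. ENI looks better by about 2.5 points.
- *36 months.* ADT men still show 0%, so ENI still looks better by 8 points.

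**The case against.** - **The plan does not commit to a pooled ENI test.** The groups are unnamed, two of the questions are framed by ADT, and adjustment for confounders is foreseen. This stands: a reader might infer that a pooled comparison is specified, and it is not. Nor is it excluded, and ADT is never named.
- **Thirty-six months is a minimum, and two to three years is background.** Both stand. The ADT duration describes typical practice in high and very high risk men; intermediate-risk men are also enrolled, and the long-term ADT share is unknown. Still, no later visit is scheduled.
- **A reader might infer that ADT will make ENI look better by 5 to 8 points.** The documents do not support this. At 24 or 30 months of ADT the gap exists only if relapse is truly delayed; if it is merely hidden and surfaces soon after stopping, 36-month rates equalise. Higher baseline risk in ADT men can reverse the sign. Only the 36-month case is insensitive to the model.
- **ADT dates and testosterone are collected.** True, and they allow a repair. But grouping men by achieved ADT duration conditions on surviving and not relapsing. The one-month form separates ADT types, not short from long intent. The follow-up section lists a total duration beside actual end dates. Attachment 3 opens mid-table in the available text, so it cannot be said firmly that no form holds intended duration.
- **PSA suppression by ADT is not stated in the documents.** It is an assumption here. Pairing testosterone with PSA is consistent with it.

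**Conclusion.** The concern holds in a limited form. Within scheduled follow-up, men on the long-term ADT that the protocol describes have 12 to 0 off-ADT months against 36, and the planned survival comparison has no ADT term. Where ENI and non-ENI groups differ in ADT use or duration, the bRFS comparison can be biased, in a direction that cannot be fixed in advance. The size ranges from negligible (24 or 30 months of ADT with prompt surfacing) to a false rejection rate near 77% (36 months, 70%/30% shares), under the assumed hazard, suppression and shares. Where ADT is the same on both sides, the cost is lost events, not bias; at 36 months of ADT there are none left to compare. The matter should be corrected, but it touches a secondary endpoint only.

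**What to change.** 1. Add planned ADT (none, or planned duration in months) to the one-month form, beside the existing item on association with hormonal therapy. If a form already holds it, name that item in the analysis text.
2. In Statistical Analyses, make the main ENI versus no-ENI comparison of bRFS stratified by planned ADT: a stratified log-rank test, or a Cox model stratified by ADT and adjusted for risk group. Under the equal-hazard assumptions above, each stratum then compares men with the same chance of showing an event. Any pooled curve is descriptive only. A ban on pooling is not needed.
3. State the bRFS definition, including how PSA under ADT is handled.
4. State that 36-month bRFS in men on long-term ADT is PSA control on ADT and supports no ENI conclusion about relapse. Supplement it with a description of relapse counted from ADT stop, using the dates already collected. Where off-ADT follow-up is too short, say that question 2 is not answered for bRFS.
5. Reconcile the Phase 3 and Attachment 3 visit lists, and confirm that the follow-up form has a testosterone field; none is visible in the available text.

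The cost is one form item and a paragraph of analysis text, with no extra patients or visits. The downside is smaller strata and a narrower bRFS claim for long-term ADT men. Three ADT strata by ENI by radical or adjuvant setting make 12 cells, about 400/12 = 33 men each, so the stratified test should carry the inference and cell-by-cell results should stay descriptive.
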